### **Justification for Waiver of Documentation of Consent:**

Clinic Staff/Providers – The research involves minimal risk to clinic staff. All staff
will be informed that participation in the interview is voluntary and may be
discontinued at any time. In addition, the research does *not* include procedures

- for which written consent is normally required outside of the research context (e.g., quality improvement efforts).
- Patients The research involves minimal risk to patients. While all patients invited to participate in an interview are, by definition, at increased risk of CVD, the research does *not* involve more than minimal risk. Patients will be informed that participation in the interview is voluntary. At any time, patients may choose to not answer specific questions or discontinue the interview, and all such requests will be immediately respected.

#### Justification for Waiver of HIPAA Authorization:

Patients – Interviews will include discussion of the patient's health information. While interviewers will not intentionally solicit PHI, it is possible that a patient might share this information during the semi-structured interview. While we could not practicably carry out this portion of the research (i.e., obtaining patient perceptions of the CV Wizard tool) without the possibility of collecting PHI, the PHI that might be collected is not the focus of our data collection efforts. Given that we will not be analyzing PHI, we will request that any identifiers be removed during the transcription process. The transcriptionist will be instructed to delete any identifiable patient information in the transcript and replace with the type of information removed (e.g., [\*Name\*]) and to delete the recording once the transcription is complete. Only transcribed interviews will be shared with the research teams at OCHIN and/or HealthPartners.

## 6. Study Procedures

### a. Study Aim 1

## Clinic Identification, Recruitment & Assignment

Clinics will be included in the recruitment pool for this study if they (1) provide primary care to adults with high CVD risk annually, and (2) have been using OCHIN's EHR for at least 18 months. Once all clinics have been recruited as outlined in Section 5.e., they will be assigned to either arm 1 or arm 2. Clinics were grouped based on the baseline number of encounters each service area had, percent of patients with hypertension, and percent of patients who use tobacco. Five randomly generated groupings were created and the grouping that created the most even distribution across both Arms was then selected to assign service areas and the clinics within each service area to an Arm.

### Programming CV Wizard to Accept OCHIN Data

Working with HealthPartners' programmers who previously disseminated CV Wizard to other large care systems, OCHIN's programmers will (1) build tables for data extraction (*e.g.*, medication, laboratory, diagnostic/problem list codes, vitals, smoking); (2) develop the interconnect routines needed to transmit EHR data to the CV Wizard web service, save response information in EHR flow sheets, and display the CDS results in the EHR; (3) create the alert to prompt CDS use in targeted patients; (4) develop "smart tools" (*e.g.*, dot phrases) to facilitate documenting CV Wizard use and results in EHR encounter notes; (5) program the dynamic order sets that are tailored to facilitate clinical actions recommended for each patient; (6) create CDS use rate feedback reports; and (7) develop a process to manage provider feedback on clinical aspects of CV Wizard.

## **Validity Testing**

Since 2007, CV Wizard's algorithms have been continuously modified, and re-validated after each modification. OCHIN programmers will validate that CV Wizard works correctly with data sent from OCHIN's EHR as follows:

- (1) OCHIN staff who routinely validate all changes made to the EHR will perform standard validation of data extracts for accuracy and completeness. This will include creating 'test patients' with variation in CVD risk factors and location of relevant data in the EHR, to assess how well CV Wizard performs with these patients. The validation team will also try to 'break' the CDS by testing how it performs with incomplete data. This will occur in a 'copy' of the Epic production environment used for testing EHR tools before they go into production.
- (2) We will conduct preliminary pilot work with 2-3 CHC clinician advisors to assess how CV Wizard performs in real (not test) patient data. We will ask them to identify 20-30 of their high CVD risk patients, run those patients' data through CV Wizard's algorithms, and review CV Wizard's results for accuracy and clinical plausibility.
- (3) Next, CV Wizard will be activated in pilot clinics served by clinician advisors, to further identify potential errors; these sites will be excluded from subsequent study randomization.
- (4) Further quality checks will occur throughout the study, via CV Wizard's feedback mechanism and built-in website monitoring routes designed to identify aberrant web service input or output. Any changes needed to the data sent to the CV Wizard website, as identified through these processes, will be reviewed by OCHIN / HealthPartners.

### Patient Engagement

CV Wizard's patient-facing component is designed to support patient engagement in CVD risk management. To improve this aspect of the tool, we will engage OCHIN's Patient Engagement Panel (PEP). This panel is comprised of >20 patients from OCHIN member CHCs who meet regularly to contribute input on research conducted at OCHIN. In months 1-6, we will meet with the PEP monthly to engage them in a user-centered process on whether and how to redesign the CV Wizard 'Patient View'.

## **Data Collection**

All outcome variables collected for analyses align with RE-AIM (Reach, Effectiveness, Adoption, Implementation, Maintenance), a widely used framework for evaluating implementation success. Below are details about the specific outcomes and measures for each. Please refer to Table 6 further below for additional information.

## **Primary Outcome Measures**

- **Study Aim 1:** Compare patients' change in reversible risk in the Arm 1 vs. Arm 2 CHCs (in months 18-35)
- **Study Aim 2**: Assess whether the revised implementation support materials expedite CDS adoption
- **Study Aim 3:** Use mixed methods to identify multi-level barriers / facilitators to adoption of the CDS tool

#### **Secondary Outcome Measures**

- **Reach: Encounters affected** % clinic encounters where CV Wizard suggests running the full risk assessment tool, i.e., identified a target patient.
- Effectiveness (impact): Patient outcomes 10-year pooled ASCVD risk score change in ASCVD risk score from baseline to last visit of study period (American College of Cardiology-ACC/ American Heart Association - AHA) 10-year pooled ASCVD risk score, 40-75 year olds
- Effectiveness (impact): Patient outcomes last BP ≤140/90 Control of individual CVD risk factors: last BP ≤140/90
- Effectiveness (impact): Patient outcomes last A1c≤8 Control of individual CVD risk factors: last A1c≤8
- Effectiveness (impact): Patient outcomes last LDL<100 Control of individual CVD risk factors: last LDL<100
- Effectiveness (impact): Patient outcomes not current smoker Control of individual CVD risk factors: not current smoker
- Effectiveness (impact): Patient outcomes last BMI ≤25 Control of individual CVD risk factors: last BMI≤25
- Adoption: CDS uptake % of encounters where care team member opts to run the CV
   Wizard risk assessment (explored as both view and print rate and just print rate)
- Implementation: User perceptions Perceived ease of use, usefulness, acceptability of CV Wizard; intent to use it.
- Maintenance over time All measures over 2.5 years of follow-up, Arm 1; 1.5 years, Arm 2.

Table 6. Impact and uptake of the CV Wizard system: Quantitative Measures		
Outcomes, per RE-AIM	Measurement	
Reach:	% clinic encounters where CV Wizard suggests running the full risk assessment tool,	
Encounters affected	i.e., identified a target patient	
Effectiveness (impact):	(i) change in ASCVD risk score (reversible risk; ACC/AHA 10-year pooled ASCVD risk	
Patient outcomes	score, 40-75 year olds; Framingham 30-year CVD risk score, 20-39 year olds).	
	(ii) Control of individual CVD risk factors: last BP ≤140/90; last A1c≤8; last LDL<100;	
	not current smoker; last BMI≤25);	
Adoption: CDS uptake	% of encounters where care team member opts to run the CV Wizard risk	
	assessment	
Implementation: User	Perceived ease of use, usefulness, acceptability of CV Wizard; intent to use it; see	
perceptions	3.3.f.ii	
Maintenance over time	All measures over 2.5 years of follow-up, Arm 1; 1.5 years, Arm 2	
Potential covariates	Measurement	
Patient demographic	Age; gender; race / ethnicity; primary language; poverty level; insurance status at	
characteristics	visit or insurance type through study period; # visits to that site / provider in last	
	year; whether visit was with patient's primary care provider; provider type. Others	
	TBD based on input from clinician advisors.	
Other patient comorbid	Renal function: diagnosed with end stage renal disease or chronic kidney disease;	
conditions	Charlson Comorbidity Score (Modified): Indicator of serious comorbid conditions	
	that may shorten life expectancy, modified to exclude CV components; depression	
	296.xx, 311.xx diagnosis. Other relevant comorbidities TBD.	
Visit type	New patient or established patient	
Provider type	Provider type (PCP or other); # in patient panel	
Other clinic factors	See Table 5; data from baseline survey	
CVD care / process	Measurement	

Recommended care	Whether care suggestions were acted on within 7 days of the encounter; e.g., if CV
that is ordered.	Wizard suggests starting a statin, we will ask whether a prescription was issued.

#### b. Study Aim 2 & 3

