### **Specific Aims**

**Aim 1.** Conduct a clinic-randomized trial of the impact of an evidence-based point-of-care CDS system on (i) overall CVD risk scores, and (ii) control of individual CVD risk factors (blood pressure; HbA1c, lipid levels; smoking; body mass index), among high CVD risk adult CHC patients.

**Aim 2.** Develop and hone need-based implementation support protocols to help Arm 1 CHCs implement the CV Wizard CDS system into their standard workflows; assess whether use of the protocols developed for Arm 1 CHCs accelerates implementation and adoption of the CDS system in the Arm 2 CHCs. **Supplement Addendum:** Compare CVD risk management in high-risk patients at in-person vs. virtual care (VC) encounters, in the periods pre- and post-COVID's onset.

**Aim 3.** Conduct a mixed methods process evaluation, guided by the Technology Acceptance Model (TAM), to identify and address patient, provider, and delivery system barriers to uptake/impact of this CDS in CHCs. **Supplement Addendum:** In a subset of study clinics, explore how CV Wizard's individualized, prioritized CVD risk summary is used in VC to guide care decisions and engage patients in shared decision-making.

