#### **Quantitative Data**

To be included in Aim 1 analyses a patient must have at least one visit in the 6 months after the Arm 1 implementation date at an Arm 1 or Arm 2 CHC and at least one additional visit at a study clinic in the 12-month post-index visit period. The first visit is referred to as the index visit. We will describe those who had inadequate follow-up data (did not have at least one additional visit in the post-index period). For each study subject, CVD risk score / risk factor management status will be calculated at index visit and each encounter during follow-up. While the tool can be run for patients of any age, we will restrict our analyses to patients 40-75 years of age.

We will test for between-group differences in baseline characteristics such as age, sex, race and ethnicity, insurance type, visit count, and health status using chi-square, t-test, and nonparametric Wilcoxon rank-sum tests as appropriate. We will also test for association between baseline characteristics and our outcomes of interest. We will examine the number of patients seen in each service area and clinic and each Arm and compare the characteristics of Arm 1 patients for whom the tool was used to those in Arm 1 for whom the tool was not used and to Arm 2 patients. Because the two arms were selected based on clinic size, percent of patients with a diagnosis for hypertension and the percent of patients that use tobacco, we anticipate there will be differences between the two groups resulting in the need to adjust for these differences. We will also examine characteristics at the service area and clinic-level in Arm 1 for whom the tool was used compared to Arm 1 service areas / clinics for whom the tool was not used and Arm 2 service areas / clinics.

Unadjusted trends in the monthly use and view rates for each of the study CHCs will be explored with use rates defined as: the number of encounters where CV Wizard was printed / number of targeted encounters with high-CVD risk patients per month and view rates defined as the number of encounters where CV Wizard was viewed / number of targeted encounters with high-CV risk patients per month.

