We will also examine overall rates of each of the impact outcomes (BMI in normal range, controlled blood pressure, controlled LDL, controlled HbA1c, and non-smoking status) pre/post tool use to assess any changes in patterns for patients in Arm 1 for whom the tool was used compared to those in Arm 1 for whom the tool was not used as well as to Arm 2 patients. The date the tool was first used for each patient will be assigned as the start of the post-period.

Extent of adoption of a CDS tool like CV Wizard directly impacts its population-level impact. To differentiate between the tool's population level impact versus impact when used, we will conduct intent to treat (ITT) analyses to compare all targeted patients at intervention versus control clinics. We will also conduct effect of treatment on the treated (ETOT; also called per protocol) analyses limited to intervention CHC patients for whom the CV Wizard tool was used (results viewed / printed out) at the index visit, compared to intervention clinic patients for whom it was not used, and separately, to control clinic patients. The ITT analyses test the hypotheses that targeted patients in intervention clinics will have significantly lower CVD risk scores and higher rates of CVD risk factor control, at visits in the year post-index visit period, compared to similar patients in control clinics. The ETOT analyses test the hypotheses that targeted patients in intervention clinics for whom the CV Wizard CDS tool results are viewed and / or printed will have significantly lower CVD risk scores and higher rates of CVD risk factor control, at visits in the year post-index visit period, compared to similar patients in control clinics, and compared to patients in intervention clinics for whom the tool alerted but was ignored at the index visit.

Analyses will be stratified by first-time and repeat patients to see if there is a difference in tool use as well as examine whether the time between visits effects tool use among repeat patients.

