### **Intent to Treat Analysis**

Differences in change in outcomes will assessed using multi-level mixed models. Intra-class correlation coefficients will be obtained at the patient, clinic, and CHC organization levels for each outcome showed that much organization-level variance could be attributed to the clinic level. Thus, clustering was accounted for by random effects for clinic and patient, and a fixed effect for organization. Analyses will adjust for fixed effects: distribution of eligible patients by age, race / ethnicity, gender, rural / urban status, and federal poverty level (FPL) at index visit; number of ambulatory visits during the follow-up period; and time from index to last visit. These variables were selected *a priori* and will be confirmed by descriptive analyses, to determine whether there are significant differences between baseline intervention and control organization and patient characteristics. After checking distributions, negative binomial mixed-models or poisson mixed-model will be used for reversible risk analyses, and linear-mixed models for all other outcomes.

Patients diagnosed with diabetes during the follow-up period will be excluded from reversible risk analyses because diabetes might be diagnosed more often with CDSS use. Presence of diabetes raises reversible risk estimations even if CVD risk factor control was addressed; this exclusion will remove the possibility of confounding based on likelihood on new diabetes diagnosis.

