#### **Effect of Treatment on the Treated Analysis**

Per-protocol analyses require adjusting for loss to follow-up and off-protocol therapies or treatments, but if group differences vary too greatly, model misspecification can yield biased estimates. Propensity score methods are an alternative. We will match intervention organization patients in three categories of tool use (never used during follow-up, used once, used more than once) to control organization patients. Counts of tool use will include use at index visit or subsequent study period visits, excluding the last visit. Matching variables will include age, FPL, outcome of interest at baseline, race / ethnicity, sex, count of ambulatory care visits post-index

visit, time from index visit to last study period visit, and clinic rural / urban status. Propensity scores will be estimated using nearest-neighbor matching with replacement.

As analyses in other settings indicated CV Wizard's potential for greater impact among patients with higher baseline risk, analyses of change in reversible risk will be stratified by baseline risk <10% or ≥10%. The assumption being that patients with lower baseline risk are less likely to improve. Additionally, we will run analyses by quartile of baseline reversible risk among patients for whom the tool was ever used during follow-up, matched to controls as described above. Analyses of change in reversible risk will include all patients meeting study inclusion / exclusion criteria; for other outcomes, analyses were restricted to patients with uncontrolled baseline risk. Linear mixed models will be used for all outcomes and checked for normality of residuals.

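### The only BMI endpoint defined for Aim 1 is a yes/no cut-off at 25, which has low power for modest weight change within a year; change in BMI should be added as the analysis of effect

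*Combined protocol and SAP*

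**What the plan says.** Aim 1(ii) under Specific Aims covers "control of individual CVD risk factors (blood pressure; HbA1c, lipid levels; smoking; body mass index"). Section 6.a, Secondary Outcome Measures, defines the BMI component as "Control of individual CVD risk factors: last BMI≤25", and Table 6 repeats it. Section 7.a, Quantitative Data, calls the same component "BMI in normal range". No endpoint based on BMI change or percent weight change is defined anywhere.

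The intent-to-treat (ITT) and treatment-on-the-treated (ETOT) hypotheses in that section both concern "higher rates of CVD risk factor control, at visits in the year post-index visit period". For inclusion, a patient needs "at least one additional visit at a study clinic in the 12-month post-index visit period", so the last BMI may come from a single early return visit. Maintenance is listed separately, as "All measures over 2.5 years of follow-up, Arm 1; 1.5 years, Arm 2".

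For the model, the Intent to Treat Analysis section assigns "linear-mixed models for all other outcomes" (all except reversible risk). The Effect of Treatment on the Treated section uses linear mixed models throughout with a check that residuals are normal, and adds that "for other outcomes, analyses were restricted to patients with uncontrolled baseline risk". Neither section says whether BMI enters as a measured value or as controlled/not controlled. The Statistical Power section deals only with the CVD risk score.

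**The concern.** Weight moves slowly, and a fixed threshold registers only patients who pass it. A patient going from BMI 35 to 31 scores the same as one who gained weight. Status can change with a modest loss only in patients who start just above 25. If the tool produces a small average loss spread over all patients, most of that benefit is invisible to the endpoint.

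At stake is what a null BMI result could mean. BMI is one of five individual risk factors named in the aim. If its comparison comes out flat, readers may conclude that the tool does not affect weight, when the endpoint had little chance of showing a small effect. The measured BMI needed for a more sensitive comparison is already in the extracted records.

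**Working it through.** **The plan's own figure.** There is none for BMI. The only power value in the documents is for the supplement (Aim 2b, CVD risk score). It reproduces: SD of change = √(9.1² + 9.1² − 2 × 0.2 × 9.1²) = 11.51; SE = 11.51 × √(2/6000) = 0.210; 5.0/0.210 = 23.8; power 100%. It has no bearing on BMI.

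**Step 1: loss needed to reach 25 (no assumptions).** Loss = 1 − 25/BMI.

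| Index BMI | 25.5 | 26 | 27 | 28 | 30 | 32 | 35 |
|---|---|---|---|---|---|---|---|
| Loss needed | 2.0% | 3.8% | 7.4% | 10.7% | 16.7% | 21.9% | 28.6% |

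**Step 2: share of all patients moved across 25 by a uniform loss L.** With index BMI assumed normal with mean m and SD s, share = Φ((25/(1 − L) − m)/s) − Φ((25 − m)/s). For m = 32, s = 7 this is 1.8% at L = 2% and 5.0% at L = 5%. Over 30/6 to 34/8 it is 1.4-2.5% and 3.8-6.7%.

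**Step 3: power among patients above 25 at index.** From the Statistical Power section: 60 clinics in two arms, taken as 30 per arm, and 35 patients per clinic (the plan says more than 35). Assumed: index BMI mean/SD 30/6 to 34/8; SD of one-year change 1-2; ICC 0.01-0.03; no mean change in control; two-sided 5% test.

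Central case (32/7, SD of change 1.5):

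- Share above 25 = 84.1%, so k = 35 × 0.841 = 29.4 per clinic and 883 per arm.
- Effective n = 883/(1 + 28.4 × ICC) = 688 at ICC 0.01, or 477 at ICC 0.03.
- Share at or below 25 at follow-up: 2.78% with no effect, 4.25% with a 2% mean loss, 7.25% with a 5% loss.
- Two-proportion power: 23-31% at 2%, 89-97% at 5%.
- Mean change at 2%: mean index BMI in this subset is 34.0, so the difference is 0.68. At ICC 0.03, SE = 1.5 × √(2/477) = 0.097 and z = 7.0, giving power of about 100%.

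Corners of the assumed range:

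| Mean/SD, SD of change, ICC | Effective n per arm | Crossing: none / 2% / 5% loss | Power at 2% | Power at 5% |
|---|---|---|---|---|
| 34/8, 2, 0.03 | 485 | 2.86% / 3.99% / 6.20% | 16% | 71% |
| 30/6, 1, 0.01 | 660 | 2.54% / 4.61% / 9.11% | 52-53% (rounding of clinic size) | about 100% |

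Across the range the indicator keeps about 1-8% of the information in BMI change (squared ratio of standardised contrasts).

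**Step 4: cross-check on the absolute scale.** With assumed index BMI 29/6 to 33/7, the same SDs of change and ICCs, and 35 patients per clinic:

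| Mean benefit (kg/m²) | Power for ≤25, all patients | Power for ≤25, index >25 |
|---|---|---|
| 0.3 | 6-11% | 8-23% |
| 0.5 | 11-25% | 16-54% |
| 1.0 | 33-72% | 51-99% |
| 1.5 | 63-97% | 85-100% |

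Mean BMI change has 98-100% power at 0.5 kg/m². These are design-effect approximations. They ignore the planned covariates and repeated visits.

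**The case against.** The strongest reply is that the endpoint is far from useless. With a 5% mean loss it has fair to high power, patients at 25.5-26 can cross with a small loss, and 35 patients per clinic is a floor. With 300 per clinic and a 0.5 kg/m² benefit, power rises to 16-58% in all patients and 26-96% in those above 25. This stands. A reader might infer that almost nobody can cross 25, or that the result must be null whatever the tool does. The documents give no BMI distribution to support the first, and the calculation contradicts the second.

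Nor do the documents establish that measured BMI is discarded. Linear mixed models and a residual-normality check suit a continuous value. The ETOT matching on the baseline outcome would also be empty if that outcome were a status already fixed as uncontrolled. Against this, the outcome list and hypotheses speak of rates of control. The fair reading is that the scale is unspecified, which itself needs correcting.

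Follow-up is also not limited to a year everywhere. Maintenance runs for 1.5-2.5 years, and the primary comparison is placed in months 18-35. But the Aim 1 hypotheses are one-year, and Arm 2 receives the tool 18 months after Arm 1, so the longer maintenance period gives no longer comparison with untreated clinics.

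Finally, the aim concerns control, and the other four factors are scored by status too. That is a good reason to keep the cut-off rather than replace it. The mismatch between ≤25 and normal range is minor: it matters only for underweight patients, who cannot be in the subset above 25.

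**Conclusion.** The point holds as a sensitivity problem in one secondary outcome. Among patients above 25 at index, the cut-off has about 16-53% power for a 2% mean loss and about 71-100% for a 5% loss, against about 100% for mean BMI change. A null result on the cut-off would be uninformative about small effects, and it is not certain to occur. All BMI inputs are assumptions, so the ranges are for orientation; the weight losses in Step 1 rest on none. The primary outcome, change in reversible risk, is not defined by this cut-off. Importance is minor, but the remedy is cheap.

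**What to change.** Keep last BMI ≤25 as the prespecified control outcome. Add change in BMI from index to last follow-up value to Secondary Outcome Measures, Table 6 and the Intent to Treat Analysis section:

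- For ITT, analyse it in all targeted patients, with those above 25 at index as a subset.
- For ETOT, analyse it in the set already restricted to patients uncontrolled at baseline.
- Use the linear mixed model already specified, with index BMI as a covariate.
- Name this as the analysis on which any conclusion about an effect on BMI rests.
- State in both analysis sections whether each BMI outcome enters as a value or a status.
- Use one definition of BMI control in Secondary Outcome Measures and in the Quantitative Data section.

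The cost is a few lines of text and one added secondary analysis, with no new data. It must be documented as an amendment before analysis.
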